**Week 25 up to 72 (for subjects receiving optional additional treatment extension)**

Patient receiving an optional additional treatment extension of up to 6 months, at the discretion of the investigator, will continue to be seen every 6 weeks after week 24 while on the study medication, then at 12 weeks and 24 weeks after completion of up to 12 months of study drug, to determine durability or response or evidence for a delayed effects.

Efficacy evaluations: SALT, PGA, Patient global assessment and patient quality of life assessment will continued to be performed at every visit during optional additional treatment extension.

Blood draws for safety parameters will be conducted at 12 weeks after completion of study drug if deemed necessary to assess normalization of any previously abnormal values.

Adverse events will be assessed at every visit.

Standardized photographs of the subject's scalp will be done at every scheduled visit and will be used to support determination of percent hair regrowth. Photography will be performed using a high-resolution digital camera with Intellistudio system from Canfield Scientific, Inc. Patients will be positioned using a laser guide, after which photographs of the entire scalp will be taken at standardized locations and at a fixed distance. Close-up photographs may also be taken using an epiluminescent attachment in order to assess for the presence of early regrowth.

### Unscheduled Visits

An unscheduled visit can occur at any time during the study for instance as prompted by signs of infection or local injection site reactions. A source document must be maintained for these unscheduled visits. The date for the visit and any data generated must be recorded on the appropriate CRF. At treatment discontinuation/early termination subjects will undergo end of study evaluations per the Schedule of Assessments.

### Telephone contact/retention

Patients will be contacted on a monthly basis, between the planned study visits at weeks 36 and 48, in the observational phase (Weeks 25 to 48, up to Week 72 for subjects receiving treatment extension) of the study to ascertain the occurrence of adverse events as well as to assess the status of hair growth or loss.

Any concerns or questions the patient may have will also be addressed. If deemed necessary, the subject may be asked to come in for an unscheduled visit.

### Duration of Treatment

After the screening period, subjects will begin weekly self-administered subcutaneous abatacept and will continue treatment for 6 months. Patients will be instructed in self-administration of study medication at baseline (week zero) and will be observed self-administering medication at each visit. Instructions regarding study drug administration will be reinforced as needed.

The 6-month treatment period is expected to provide adequate time to assess the short-term efficacy and safety of abatacept in patients with moderate to severe AAP. Responders will then be followed for 6 months off drug.

Treatment may be extended by up to an additional 6 months beyond the initial 6 months of treatment if clinically indicated at the discretion of the investigator.

## **4.2 Study Population**

For entry into the study, the following criteria **MUST** be met. Any exceptions must be approved by the Principal Investigator and/or IRB/IEC before enrollment.

### **4.2.1 Inclusion Criteria**

#### **1) Signed Written Informed Consent**

Before any study procedures are performed, subjects will have the details of the study described to them, and they will be given a written informed consent document to read.

Then, if subjects consent to participate in the study, they will indicate that consent by signing and dating the informed consent document in the presence of study personnel.

- 2) Must be between 18 and 75 years of age.
- 3) Must have a diagnosis of moderate to severe AA - defined as the presence of equal to or more than 30% and equal to or less than 95% total scalp hair loss at baseline as measured using the SALT score. Five patients with current alopecia totalis/universalis may be included in this study at the investigator's discretion.
- 4) Duration of hair loss greater than 3 months without an upper limit of duration as long as there is reason to believe that regrowth is possible in the opinion of the investigator.
- 5) No evidence of active, ongoing regrowth present at baseline.
- 6) Patients with alopecia totalis/universalis can be included as long as the current episode of hair loss meets the criteria of 30 to 95% hair loss (i.e. they may have had a previous episode of AT or AU which demonstrated regrowth of hair, and they are not currently AT or AU), and as long as in the opinion of the investigator there does appear to be potential for regrowth. Two to five patients with current episodes of alopecia totalis/universalis may be included in this study at the investigator's discretion.
- 7) Subjects may be naïve to treatment or unresponsive to intralesional (IL) steroids or other treatments for AA.
- 8) Must be willing to avoid live vaccines while on the study medication, and within 3 months of its discontinuation.
- 9) Women of childbearing potential (WOCBP) must use highly effective methods of birth control [for up to 12 weeks after the last dose of investigational product] to minimize the risk of pregnancy]. WOCBP must follow instructions for birth control for the entire duration of the study including a minimum of 90 days after dosing has been completed.
  - a. Acceptable methods of highly effective birth control include:
    - i. Condom with spermicide
    - ii. Diaphragm and spermicide
    - iii. Cervical cap and spermicide
  - b. The use of intrauterine devices, (IUDs) shall be at the discretion of the investigator.
  - c. Women must have a negative serum or urine pregnancy test (minimum sensitivity 25 IU/L or equivalent units of HCG) within 24 hours prior to the start of investigational product.
  - d. Women must not be breastfeeding
- 10) Sexually active fertile men must use highly effective birth control if their partners are WOCBP. Men that are sexually active with WOCBP must follow instructions for birth control for the entire duration of the study and a minimum of 90 days after dosing has been completed.

#### **4.2.2 Exclusion Criteria**

##### **1) Sex and Reproductive Status**

- a. WOCBP who are **unwilling or unable** to use an acceptable method to avoid pregnancy for the entire study period and for up to 10 weeks after the last dose of study drug.
- b. WOCBP using a prohibited contraceptive method.
- c. Women who are pregnant or breastfeeding.
- d. Women with a positive pregnancy test on enrollment or before administration of abatacept.
- e. Sexually active fertile men not using effective birth control if their partners are WOCBP.

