| 
Inclusion Criteria:
 | 
Patients between 18 to 75 years of age.
 
Patients with a diagnosis of moderate-to-severe patch type alopecia areata.
 
Patients will have <math>\geq 30\%</math> and <math>< 95\%</math> total scalp hair loss at baseline as measured using the SALT score.
 
Patients with alopecia totalis/universalis can be included as long as the current episode of hair loss meets the criteria of 30 to 95% hair loss (i.e. they are not currently AT or AU), and as long as in the opinion of the investigator there appears to be potential for regrowth.
 
Two to five patients with current episodes of alopecia totalis /or universalis (100% scalp hair loss) may be included in this study at the discretion of the investigator.
 
Duration of hair loss greater than 3 months without an upper limit of duration as long as there is reason to believe that regrowth is possible in the opinion of the investigator.
 
No evidence of active/ongoing regrowth present at baseline.
 
Patients may be naïve to treatment or unresponsive to intralesional (IL) steroids or other treatments for alopecia areata.
 |
|-----------------------------------|--|

|                                   |   |
|-----------------------------------|---|
| 
Exclusion Criteria:
 | 
Two to five patients with alopecia totalis/universalis at the time of enrollment at the discretion of the investigator.
 
Patients with a history of or active skin disease on the scalp such as psoriasis or seborrheic dermatitis.
 
Patients in whom the diagnosis of alopecia areata is in question.
 
Patients with active medical conditions or malignancies (except adequately treated basal or squamous cell carcinoma) that in the opinion of the investigator would increase the risks associated with study participation, including patients with a history of recurrent infections.
 
Women of childbearing potential who are unable or unwilling to use two forms of birth control for the study duration.
 
Women who are pregnant or nursing.
 
Patients with COPD
 
Patients known to be HIV or hepatitis B or C positive.
 
Patients with history or evidence of hematopoietic abnormality.
 
Patients with history of immunosuppression or history of recurrent serious infections.
 
Patients unwilling or unable to discontinue treatments known to affect hair regrowth in AA.
 |

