### **4.4 Discontinuation of Subjects from Treatment**

Subjects MUST discontinue study treatment and withdraw from the study for any of the following reasons:

Withdrawal of informed consent (subject's decision to withdraw for any reason)

Any clinical adverse event (AE), laboratory abnormality, or intercurrent illness which, in the opinion of the investigator, indicates that continued participation in the study is not in the best interest of the subject

Pregnancy

- Instruct WOCBP to contact the investigator or study staff immediately if they suspect they might be pregnant (eg, missed or late menstrual period) at any time during study participation. Institutional policy and local regulations should determine the frequency of on-study pregnancy tests for WOCBP enrolled in the study.
- The investigator must immediately notify BMS if a study subject becomes pregnant. The mechanism for reporting pregnancy is described in Section 7.6.

Termination of the study by BMS.

Loss of ability to freely provide consent through imprisonment or involuntarily incarceration for treatment of either a psychiatric or physical (eg, infectious disease) illness.

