## 6.10 Pregnancy

Sexually active WOCBP must use an effective method of birth control during the course of the study, in such a manner that the risk of failure is minimized. (See Section 4.2.1 for the definition of WOCBP.) Before enrolling WOCBP in this study, investigators must review the BMS-provided information about study participation for WOCBP, which can also be found in the GCP Manual for Investigators. The topics include the following:

General Information

Informed Consent Form

Pregnancy Prevention Information Sheet

Drug Interactions with Hormonal Contraceptives

Contraceptives in Current Use

Guidelines for the Follow-up of a Reported Pregnancy.

Before study enrollment, WOCBP must be advised of the importance of avoiding pregnancy during study participation and of the potential risk factors for an unintentional pregnancy. The subject must sign an informed consent form documenting this discussion.

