### 6.10.1 Requirements for Pregnancy Testing

**All WOCBP MUST have a negative pregnancy test within 72 hours before receiving abatacept.** The minimum sensitivity of the pregnancy test must be 25 IU/L or equivalent units of HCG. If the pregnancy test is positive, the subject must not receive abatacept and must not continue in the study.

**In addition, all WOCBP must be instructed to contact the investigator and/or other study personnel immediately if they suspect they might be pregnant (eg, missed or late menstrual period) at any time during study participation.**

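### The contraception period after the last dose is stated in four conflicting ways, and women are told to report a suspected pregnancy only while they are in the study

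*Combined protocol and SAP*

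**What the plan says.** Five statements set the contraception period for women of childbearing potential:

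- Synopsis, Exclusion Criteria: "Women of childbearing potential who are unable or unwilling to use two forms of birth control for the study duration". No period after the last dose.
- Section 6.10: "Sexually active WOCBP must use an effective method of birth control during the course of the study". No period after the last dose.
- Section 4.2.2 item 1a: "an acceptable method to avoid pregnancy for the entire study period and for up to 10 weeks after the last dose of study drug".
- Section 4.2.1 item 9, first sentence: "for up to 12 weeks after the last dose of investigational product".
- Section 4.2.1 item 9, next sentence: the whole study, "including a minimum of 90 days after dosing has been completed".

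Item 10 of Section 4.2.1 sets the same 90-day minimum for men with partners of childbearing potential.

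On reporting, Section 4.4 has women contact the site "immediately if they suspect they might be pregnant (eg, missed or late menstrual period) at any time during study participation", and Section 6.10.1 repeats the instruction with the same limit, "at any time during study participation". Section 4.4 opens with "Subjects MUST discontinue study treatment and withdraw from the study for any of the following reasons"; the list includes adverse events that make continuing inadvisable. The investigator's duty runs longer: Section 6.10.2 covers a pregnancy exposed to the drug up to at least six half-lives after administration, and Section 6.5.1 requires every pregnancy to be reported.

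**The concern.** The statements cannot all be followed. Item 9 alone sets a ceiling of 84 days and a floor of 90. A woman willing to use contraception for only ten weeks after her last dose passes exclusion 1a and fails inclusion item 9. No sentence says which text takes precedence.

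The reporting instruction has a different gap. A woman taken off drug for an adverse event must also leave the study, so her participation can end at or soon after her last dose. The protocol then gives her no instruction to report a pregnancy, while the investigator must still report one exposed within six half-lives. At stake is an unreported exposed pregnancy in someone who left early. No efficacy endpoint, analysis or power figure is involved.

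**Working it through.** The plan states no calculated figure to reproduce. The check converts each period to days and compares it with the Section 6.10.2 exposure window.

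**Inputs.** Mean half-life after subcutaneous dosing in healthy adults is 11.2 to 14.7 days, and after intravenous dosing in rheumatoid arthritis 13 to 14 days (Section 1.3.2). In subjects with an immune response to abatacept it is 3.2 to 7.5 days; 11 of 40 had such a response after a single subcutaneous dose (Section 1.3.4). The window is at least six half-lives (Section 6.10.2).

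**Periods.** 10 × 7 = 70 days; 12 × 7 = 84 days; the stated minimum is 90 days. The two ceilings fall 90 − 70 = 20 and 90 − 84 = 6 days below the floor.

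**Margin = stated period − 6 × half-life, in days:**

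| Half-life | 6 half-lives | 10 weeks (70) | 12 weeks (84) | 90 days |
|---|---|---|---|---|
| 11.2 | 67.2 | +2.8 | +16.8 | +22.8 |
| 13 | 78.0 | −8.0 | +6.0 | +12.0 |
| 14 | 84.0 | −14.0 | 0.0 | +6.0 |
| 14.7 | 88.2 | −18.2 | −4.2 | +1.8 |

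**Longest half-life each period covers = period ÷ 6:** 70 ÷ 6 = 11.67 days; 84 ÷ 6 = 14.0 days; 90 ÷ 6 = 15.0 days. Only 90 days covers the documented range of means. With an immune response, six half-lives is 6 × 3.2 = 19.2 to 6 × 7.5 = 45 days, and every stated post-dose period is long enough.

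**Who is covered anyway.** A woman who completes the off-drug follow-up stays in the study for 24 × 7 = 168 days after her last dose, longer than any stated period and than the window. The gap is confined to women who leave earlier. That includes withdrawals under Section 4.4. It may include nonresponders, because Section 4.1 keeps them in follow-up while Section 6.4.2 does not require them to stay (it does keep partial responders).

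**Other ways a pregnancy could be detected.** Table 3 schedules a urine pregnancy test at week 24 or early termination, but none at 12 or 24 weeks after treatment. Section 6.7.1 requires collection of all serious events for 30 days after the last dose, which ends 67.2 − 30 = 37.2 to 88.2 − 30 = 58.2 days before the six-half-life window closes. After a woman leaves, her own report is the main source left.

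**The case against.** The strongest reply is that the operative rule can be worked out. The closing paragraph of Section 4.2.2 requires every eligibility criterion to be met, so the 90-day minimum binds, and passing exclusion 1a permits nothing that item 9 forbids. The 12-week phrase sits in unbalanced square brackets and looks like template residue. Item 9 can also be read as placing the 90 days inside the study, which would reconcile the synopsis and Section 6.10. This largely stands: 90 days is very probably the intent, and item 10 supports it. But the reader has to infer it, and exclusion 1a and item 10 treat the study and the post-dose period as separate.

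Second, six half-lives is the protocol's window for reporting exposed pregnancies, not a stated standard for contraception. Section 4.2.2 item 5a refers to five half-lives for prior investigational drugs, and 5 × 14 = 70 days is exactly ten weeks. That is fair. The shortfalls above measure misalignment with Section 6.10.2, not breach of a contraception standard. The half-lives are also means, so 90 days would not cover an individual above 15.0 days.

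Third, adverse events that lead to discontinuation are followed up (Sections 6.7.1 and 6.7.3), pregnancies are handled as serious events, and the consent form and Pregnancy Prevention Information Sheet may already state 90 days. Those follow-up duties bind the investigator and make some later contact likely. They do not tell the woman to report. The subject-facing texts are not among the documents, so no actual exposure is shown.

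**Conclusion.** The concern holds as a minor error in the safety text. Five statements give four periods, two of which are irreconcilable within one inclusion item, and the subject's reporting instruction stops at the end of participation, which Section 4.4 can bring forward to about the last dose. Measured against Section 6.10.2, ten weeks is 8 to 18.2 days short at half-lives of 13 to 14.7 days, twelve weeks is at most 4.2 days short, and 90 days is sufficient.

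This rests on the protocol's mean half-lives and on taking the six-half-life window as the reference. The number of women affected cannot be estimated from the documents and may be zero: on contraception, a woman is affected only if she leaves early, the site applies a text shorter than item 9, and the subject information does not correct it. Confidence is high on the textual conflict and on the limit of the reporting instruction. No endpoint, sample size or analysis changes.

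**What to change.** Put one rule in the synopsis, Section 4.2.1 item 9, Section 4.2.2 item 1a and the first sentence of Section 6.10: *until 90 days after the last dose of abatacept or the end of study participation, whichever is later*. Delete the 12-week phrase from item 9 and the 10-week phrase from item 1a.

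In Section 6.10.1 and the matching bullet of Section 4.4, replace "at any time during study participation" with *up to the end of study participation or 90 days after the last dose of abatacept, whichever is later*.

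The cost is six wording changes in one amendment, plus a check that the consent form and the Pregnancy Prevention Information Sheet say the same. No visit, test or telephone call is added, and sample size, power and analysis are untouched.

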## 2) **Target Disease Exceptions**

- a. Two to five patients with current alopecia totalis/universalis at the time of enrollment (i.e. 100% scalp or 100% scalp and body loss, respectively) may be enrolled. The remaining patients must have 30 to 95% hair loss due to alopecia areata.
- b. Patients with a history of or active skin disease on the scalp such as psoriasis or seborrheic dermatitis.
- c. Patients in whom the diagnosis of alopecia areata is in question.
- d. Patients with active medical conditions or malignancies (except adequately treated basal or squamous cell carcinoma) that in the opinion of the investigator would increase the risks associated with study participation, including patients with a history of recurrent infections.
- e. Patients with COPD
- f. Patients known to be HIV or hepatitis B or C positive.
- g. Patients with history or evidence of hematopoietic abnormality.
- h. Patients with history of immunosuppression or history of recurrent serious infections.
- i. Patients unwilling or unable to discontinue treatments known to affect hair regrowth in AA

## 3) **Coexisting disease or concurrent medications**

- a. Patients taking TNF antagonists or other biological therapy such as anakinra.
- b. Patients known to be HIV or hepatitis B or C positive.
- c. Patients with evidence of infection or active/untreated skin cancer.
- d. Patients who have been treated with intralesional steroids, systemic steroids, anthralin, squaric acid, DPCP (diphenylcycloprophenone), topical, minoxidil or other medication which in the opinion of the investigator may affect hair regrowth within one month of the baseline visit.

- e. Subjects who are impaired, incapacitated, or incapable of completing study-related assessments.
- f. Subjects with current symptoms of severe, progressive, or uncontrolled renal, hepatic, hematologic, gastrointestinal, pulmonary, cardiac, neurologic, or cerebral disease, which, in the opinion of the investigator, might place a subject at unacceptable risk for participation in the study.
- g. Female subjects who have had a breast cancer screening that is suspicious for malignancy and in whom the possibility of malignancy cannot be reasonably excluded by additional clinical, laboratory, or other diagnostic evaluations.
- h. Subjects with a history of cancer in the last 5 years, other than non-melanoma skin cancers cured by local resection or carcinoma in situ. Existing non-melanoma skin cancers should be removed, the lesion site healed, and residual cancer ruled out before administration of the study drug.
- i. Subjects who currently abuse drugs or alcohol.
- j. Subjects with evidence (as assessed by the investigator) of active or latent bacterial or viral infections at the time of potential enrollment, including subjects with evidence of human immunodeficiency virus (HIV) detected during screening.
- k. Subjects with herpes zoster or cytomegalovirus (CMV) that resolved less than 2 months before the informed consent document was signed.
- l. Subjects who have received any live vaccines within 3 months of the anticipated first dose of study medication.
- m. Subjects with any serious bacterial infection within the last 3 months, unless treated and resolved with antibiotics, or any chronic bacterial infection (eg, chronic pyelonephritis, osteomyelitis, or bronchiectasis).
- n. Subjects at risk for tuberculosis (TB). Specifically excluded from this study will be subjects with a history of active TB within the last 3 years, even if it was treated; a history of active TB greater than 3 years ago, unless there is documentation that the prior anti-TB treatment was appropriate in duration and type; current clinical, radiographic, or laboratory evidence of active TB; and latent TB that was not successfully treated ( $\geq 4$  weeks).

**4) Physical and Laboratory Test Findings**

- a. Subjects must not be positive for HIV, hepatitis B or C.
- b. Subjects who are positive for hepatitis C antibody if the presence of hepatitis C virus was also shown with polymerase chain reaction or recombinant immunoblot assay.
- c. Subjects with any of the following laboratory values

- i. Hemoglobin < 10.0 g/dL
- ii. WBC < 3500/mm^3 (< 3 x 10^9/L)
- iii. Platelets < 120,000/mm^3 (< 3 x 10^9/L)
- iv. Serum creatinine > 2 times the ULN
- v. Serum ALT or AST > 2 times the ULN
- vi. Any other laboratory test results that, in the opinion of the investigator, might place a subject at unacceptable risk for participation in the study.

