## **4 INVESTIGATIONAL PLAN**

### **4.1 Study Design and Duration**

#### **Screening**

A complete medical history will be taken. Patients will be screened for pre-existing renal (basic metabolic and urine analysis), hematologic (CBC with differential and reticulocytes) or hepatic dysfunction or COPD; lipid panel; prior exposure to tuberculosis (PPD and CXR) or hepatitis; pregnancy tests will be done in women of childbearing potential.

**Assessments:** Baseline assessments of disease severity will be done. This will include SALT score (Severity of Alopecia Tool, Addendum 1), Physician global assessment (PGA), patient global assessment and patient quality of life assessment. In order to minimize or eliminate inter-rater variability, every effort will be made to have the same investigator evaluate an individual subject at each visit. Whenever possible the same investigator (the PI or her designee) will examine the patient's scalp, determine the SALT score, and grade the photographic images.

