**6) Other Exclusion Criteria**

- a. Prisoners or subjects who are involuntarily incarcerated.
- b. Subjects who are compulsorily detained for treatment of either a psychiatric or physical (e.g, infectious disease) illness.

Eligibility criteria for this study have been carefully considered to ensure the safety of the study subjects and to ensure that the results of the study can be used. It is imperative that subjects fully meet all eligibility criteria.

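### The per-litre limits in brackets for white cells and platelets do not match the per-mm³ limits beside them, so a white-cell count of 3.0 to just under 3.5 × 10⁹/L is both excluded and not excluded

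*Combined protocol and SAP*

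**What the plan says.** Item 4(c) of Section 4.2.2 (Physical and Laboratory Test Findings) opens with "Subjects with any of the following laboratory values" and lists six entries, any one of which excludes the candidate. Entry ii is "WBC < 3500/mm 3 (< 3 x 10 9 /L" and entry iii is "Platelets < 120,000/mm 3 (< 3 x 10 9 /L". In both, the mm and the 10 carry superscripts (mm³, 10⁹) that the quotes show on the line.

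The criteria are meant to bind. Section 4.2 states "For entry into the study, the following criteria MUST be met", and allows exceptions only with approval from the Principal Investigator and/or the ethics committee before enrolment. Section 4.2.2 closes with "It is imperative that subjects fully meet all eligibility criteria".

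The other provisions that bear on blood counts carry no number:

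- the screening work-up in Section 4.1, which covers "hematologic (CBC with differential and reticulocytes) or hepatic dysfunction or COPD";
- item 2(g), "Patients with history or evidence of hematopoietic abnormality";
- item 4(c)(vi), "Any other laboratory test results that, in the opinion of the investigator, might place a subject at unacceptable risk".

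The exclusion list in the synopsis has no laboratory cut-offs.

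**The concern.** A limit stated in two units should be one limit. Here the bracketed figure is the same on both lines, 3 × 10⁹/L, and equals neither of the limits it is supposed to restate.

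The platelet mismatch is too gross to mislead; the figure was probably copied from the line above. The white-cell mismatch is different, because 3.0 and 3.5 × 10⁹/L are both believable entry limits. Someone reading a laboratory report in 10⁹/L could naturally compare it with the bracket and admit a candidate whom the leading figure excludes. The documents do not state which unit the laboratory reports.

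What is at stake is the eligibility decision and the safety screen. Section 1.3.3 names infection, sometimes serious or fatal, among the risks of abatacept. Section 1.3.4 describes a grade 4 Pneumocystis pneumonia on the same weekly 125 mg subcutaneous dose. The documents do not link that case to a low white-cell count, but it shows why a screening limit of this kind should have one reading. A subject admitted under the bracket would breach the leading limit without anyone seeing that an exception was needed.

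**Working it through.** **Inputs.** From Section 4.2.2, item 4(c): white cells below 3500/mm³, bracket 3 × 10⁹/L; platelets below 120,000/mm³, bracket 3 × 10⁹/L. From the synopsis and Section 7.1: 15 subjects.

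**Conversion.** One litre is 10⁶ mm³, so the count in 10⁹/L is the count per mm³ × 10⁶ / 10⁹, that is, the count per mm³ divided by 1000.

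| Count | Leading limit (/mm³) | Converted (10⁹/L) | Printed bracket (10⁹/L) | Bracket as /mm³ | Converted ÷ bracket |
|---|---|---|---|---|---|
| White cells | 3,500 | 3.5 | 3 | 3,000 | 1.17 |
| Platelets | 120,000 | 120 | 3 | 3,000 | 40 |

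Neither printed bracket is reproduced. For white cells the bracket is 500/mm³ below the leading limit: 500 / 3500 = 14%.

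**Where the two white-cell limits disagree.**

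| White cells (10⁹/L) | Excluded by the /mm³ limit | Excluded by the bracket |
|---|---|---|
| 2.9 | yes | yes |
| 3.0 | yes | no |
| 3.2 | yes | no |
| 3.49 | yes | no |
| 3.5 | no | no |

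The conflict covers counts from 3.0 up to, but not including, 3.5 × 10⁹/L. Read literally, the platelet limits conflict from 3 to just under 120 × 10⁹/L, but 3 × 10⁹/L is not credible as an entry limit.

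**How often it could arise.** The documents give no distribution of white-cell counts, so the share p of candidates in the band is an assumption. With n = 15, the expected number is 15p and the chance of at least one is 1 − (1 − p)¹⁵.

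| Assumed p | Expected number of 15 | Chance of at least one |
|---|---|---|
| 1% | 0.15 | 1 − 0.99¹⁵ = 0.140 |
| 2% | 0.30 | 1 − 0.98¹⁵ = 0.261 |
| 5% | 0.75 | 1 − 0.95¹⁵ = 0.537 |

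These are chances that a count falls in the band. A wrong enrolment also requires staff to follow the bracket and the unnumbered safeguards to let the candidate through.

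**The case against.** The best reply is that a careful reader would resolve the conflict correctly. The leading figure comes first, the bracket is only a gloss, and the same implausible value on the platelet line warns that the brackets are unreliable. A count of 3.2 × 10⁹/L does satisfy the leading text and so is excluded on the safer reading. This is sensible practice, and the fix adopts it, but the protocol does not say it. A bracket copied down to the platelet line does not show that the white-cell bracket was itself unintended.

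A second reply points to the other safeguards. Items 2(h), 3(c), 3(j) and 3(m) exclude immunosuppression and various infections. Laboratory tests recur at weeks 4, 12 and 24, and Section 5.3.1 requires interruption for toxicity that puts the subject at risk. Together with the unnumbered provisions already quoted, these make enrolment at very low platelets unlikely and limit the harm from a mildly low white-cell count. They do not settle the limit, and item 4(c)(vi) concerns results other than those listed, so it cannot break the tie. The exception route in Section 4.2 helps only if someone recognises that an exception is needed.

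Third, Section 1.3.3 also reports serious adverse events at rates similar to placebo and no rise in serious infection with longer exposure. Nothing in the documents ties a count in the disputed band to added risk on abatacept. That stands, and it keeps the concern modest. So does the point that the prevalence range is assumed and should not be read as a rate of error.

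**Conclusion.** The concern holds. Both bracketed values are wrong as conversions: by 14% for white cells and by a factor of 40 for platelets. The platelet error is evident on its face. The white-cell error leaves a mandatory safety exclusion with two contradictory readings over a band 500/mm³ wide, and no other text resolves it.

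The conversions rest on no assumption. The 14% to 54% chance that at least one of 15 subjects falls in the band rests wholly on an assumed prevalence of 1% to 5%, and is at most an upper bound on wrong enrolments under that assumption. The sample size of 15, the stated power of 80.7% and the significance level are unaffected. The correction should be made because the criterion can reverse an eligibility decision, but it does not threaten the trial's inference.

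**What to change.** Keep the stricter per-mm³ limits and correct the brackets in Section 4.2.2, item 4(c):

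- white cells < 3500/mm³ (< 3.5 × 10⁹/L);
- platelets < 120,000/mm³ (< 120 × 10⁹/L).

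If the sponsor and the investigator intended a different single limit, such as 3000/mm³ for white cells, they should document that and state it identically in both units. Any screening blood counts already on file should then be compared with the corrected limits, so that an unrecognised eligibility deviation is found and recorded.

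The cost is a two-line protocol correction and a look at the screening counts of at most 15 subjects at one centre.
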